1 SYNOPSIS

This Statistical Analysis Plan (SAP) describes the planned analysis and reporting for the Pediatric Trials Network protocol NICHD-2014-FUR01, “Safety of Furosemide in Premature Infants at Risk of Bronchopulmonary Dysplasia” sponsored by the Eunice Kennedy Shriver National Institute of Child Health and Human Development (NICHD).

The structure and content of this SAP provides sufficient detail to meet the requirements identified by the Food and Drug Administration, European Medical Agency, and International Conference on Harmonization (ICH) of Technical Requirements for Registration of Pharmaceuticals for Human Use: Guidance on Statistical Principles in Clinical Trials [1]. All work planned and reported for this SAP will follow internationally accepted guidelines, published by the American Statistical Association [2] and the Royal Statistical Society [3], for statistical practice.

The planned analyses identified in this SAP may be included in a clinical study report (CSR), other regulatory submissions, or future manuscripts. Also, post-hoc exploratory analyses not identified in this SAP may be performed to further examine study data. Any post-hoc, or unplanned, exploratory analyses performed will be clearly identified as such in the final CSR, if applicable.

The following documents were reviewed in preparation of this SAP:

- Clinical Research Protocol for FUR01 (Version 5.0, issued 7 April 2015).
- Case report forms (CRFs) for Protocol NICHD-2014-FUR01.
- ICH Guidance on Statistical Principles for Clinical Trials (E9).

The clinical protocol, and other identified documents, should be referenced for details on the planned conduct of this study. Operational aspects related to collection and timing of planned assessments are not repeated in this SAP unless relevant to the planned analyses.

1.1 Study Synopsis

Protocol Title	Safety of Furosemide in Premature Infants at Risk of Bronchopulmonary Dysplasia (BPD)
Phase:	II
Protocol Version	Version 5.0, 7 April 2015
Product	Furosemide
Objective	Primary: Describe the safety of furosemide in premature infants at risk of BPD Secondary: Preliminary effectiveness and pharmacokinetics (PK) of furosemide
Study Design	Multi-center, randomized, placebo-controlled, dose escalating, double masked, safety study

Study Population	
Inclusion Criteria
 
 1. Documented informed consent from legal guardian, prior to study procedures 2. Receiving positive airway pressure (nasal continuous airway pressure, nasal intermittent positive pressure ventilation, or nasal cannula flow > 1LPM) or mechanical ventilation (high frequency or conventional) 3. < 29 weeks gestational age at birth 4. 7-28 days postnatal age at time of first study dose 
Exclusion Criteria
 
 1. Exposure to any diuretic ≤ 72 hours prior to first study dose 2. Previous enrollment and dosing in current study, “Safety of Furosemide in Premature Infants at Risk of Bronchopulmonary Dysplasia” 3. Hemodynamically significant patent ductus arteriosus, as determined by the investigator 4. Major congenital anomaly (e.g. congenital diaphragmatic hernia, congenital pulmonary adenomatoid malformation) 5. Meconium aspiration syndrome 6. Known allergy to any diuretic 7. Serum creatinine >1.7 mg/dl < 24 hours prior to randomization 8. BUN >50 mg/dl < 24 hours prior to randomization 9. Na <125 mmol/L < 24 hours prior to randomization 10. K ≤2.5 mmol/L < 24 hours prior to randomization 11. Ca ≤ 6 mg/dL < 24 hours prior to randomization 12. Indirect bilirubin >10 mg/dl < 24 hours prior to randomization 13. Any condition which would make the participant, in the opinion of the investigator, unsuitable for the study 																												
Number of Participants	120																												
Number of Sites	Approximately 30 sites																												
Duration of Participation:	Up to 35 days (28 days of study drug plus 7 days of safety monitoring). Information about hospitalization will be collected at 36 weeks post menstrual age and/or at discharge.																												
Dose Schedule:	
Table. N and dosing scheme
 
  
 		N	Furosemide (IV)	Furosemide (enteral)	N	Cohort N	
   
 Cohort 1	Placebo	10	1 mg/kg q 24 hours	2 mg/kg q 24 hours	30	40	
 
 Cohort 2	Placebo	10	1 mg/kg q 6 hours	2 mg/kg q 6 hours	30	40	
 
 Cohort 3	Placebo	10	2 mg/kg q 6 hours	4 mg/kg q 6 hours	30	40	
  
			N	Furosemide (IV)	Furosemide (enteral)	N	Cohort N	Cohort 1	Placebo	10	1 mg/kg q 24 hours	2 mg/kg q 24 hours	30	40	Cohort 2	Placebo	10	1 mg/kg q 6 hours	2 mg/kg q 6 hours	30	40	Cohort 3	Placebo	10	2 mg/kg q 6 hours	4 mg/kg q 6 hours	30	40
		N	Furosemide (IV)	Furosemide (enteral)	N	Cohort N																							
Cohort 1	Placebo	10	1 mg/kg q 24 hours	2 mg/kg q 24 hours	30	40																							
Cohort 2	Placebo	10	1 mg/kg q 6 hours	2 mg/kg q 6 hours	30	40																							
Cohort 3	Placebo	10	2 mg/kg q 6 hours	4 mg/kg q 6 hours	30	40																							

2 STUDY OBJECTIVES AND OUTCOMES

2.1 Objectives

Primary: Describe the safety of furosemide in premature infants at risk of BPD.
Secondary: Preliminary effectiveness and pharmacokinetics (PK) of furosemide.

2.2 Outcomes

2.2.1 Primary Outcome Measures

Safety as determined by adverse events experienced by the participants.

2.2.2 Secondary Outcome Measures

2.2.2.1 Preliminary effectiveness: Risk of BPD

The outcome measure is change in moderate-severe BPD or death risk from baseline. Moderate-severe BPD or death risk will be defined by the NICHD Neonatal Research Network BPD outcome estimator⁴. (<https://neonatal.rti.org/index.cfm?fuseaction=BPDCalculator.start>).

2.2.2.2 Pharmacokinetics

A population PK analysis will be performed. Using the final population PK model, empirical Bayesian estimates of clearance (CL), volume of distribution (V), half-life, and exposure metrics (e.g. AUC, maximum concentration) will be generated for each patient.

2.2.3 Other safety and efficacy outcomes

Death, BPD, nephrocalcinosis/nephrolithiasis, and hearing loss will be assessed.

3 STUDY METHODS

3.1 Overall Study Design and Plan

This study is a multi-center, randomized, placebo-controlled, dose escalating, double masked, safety study.

This study will consist of a screening for eligibility, a 28-day treatment period, a 7-day safety follow-up period, a 36-week PMA assessment and a final study assessment.

3.2 Selection of Study Population

Premature infants (inpatient in neonatal intensive care units) will be randomized 3:1 to furosemide: placebo with increasing target doses of furosemide for each Cohort. There will be 40 randomized and dosed participants in each Cohort for a total of up to 120 participants.

3.3 Level of Masking

The study will remain double-masked throughout the complete study period. Individual participant treatment assignments will be maintained by DCC unblinded staff only. Any unplanned unmasking occurring during the study period will be documented and reported in the final CSR.

4 ANALYSES AND REPORTING

4.1 Dose Escalation and Halting Criteria

The trial will be halted (paused) for a safety review by the Data Monitoring Committee (DMC) if there are 4 or more Serious Adverse Reactions within a given Cohort (i.e., Cohort 1, 2, or 3). If there are <4 Serious Adverse Reactions total, the DMC will receive a summary of masked safety data and enrollment will continue in the next highest dose Cohort. Enrollment in the next highest dose Cohort will begin immediately after the 40th (or 80th) subject is enrolled and the following criteria have been met:

Table 1 Rules for advancing to next highest dose Cohort

Number of Serious Adverse Reactions	% total evaluable safety days* completed from lower dose Cohort
3	100%
2	95%
1	80%
0	70%

*% total evaluable safety days = $\frac{\text{sum of days of dosing} + 7 \text{ days of safety follow up for all participants}}{\# \text{ of participants} \times 35}$

If a 4th Serious Adverse Reaction occurs in the lower dose Cohort after enrollment begins in higher dose Cohort, enrollment will be halted for safety review but current subject dosing will continue pending DMC review. If there are 4 or more Serious Adverse Reactions, then the DMC may choose to be unmasked to treatment assignment.

4.2 Interim Analyses

A masked interim safety analysis will be performed after completion of the safety follow up period of Cohort 1 participants, and again after completion of the safety follow up period of Cohort 2 participants to include data entered up to the cutoff time point (data from next Cohort will be included if entered before the cutoff time point). Enrollment will not be halted during the analyses. Halting may occur if analysis shows a positive finding. The number and percent of AEs and SAEs within each dose group will be summarized overall as well as by each Medical Dictionary for Regulatory Activities (MedDRA) system organ class and preferred term. BPD, nephrocalcinosis/nephrolithiasis, and hearing loss will be included in the summary. Also, laboratory adverse events will be tabulated by cohort.

4.3 Final Analysis

All final, planned analyses identified in this SAP will be performed only after the last subject has completed the last study visit and end of study assessments, and all relevant study data have been processed and integrated into the analysis database. In addition, no database may be locked or analyses completed until this SAP has been approved. Unmasking of treatment assignments will not occur until the data are locked.

5 SAMPLE SIZE DETERMINATION

The sample size of 30 in each dose group is sufficient to estimate AE or SAE incidence with sufficient precision. Table 2 provides widths for 95% Wilson confidence intervals in the dose groups of size 30 and the total furosemide treatment cohort of 90 with different incidence rates.

An event with an incidence rate of 0.05 has a 79% chance of being observed at least once in a dose group and a 99% chance of being observed at least once in the total furosemide Cohort.

Table 2. Widths for 95% Wilson confidence intervals.

N=30		N=90	
Rate	Width	Rate	Width
0.1	0.22	0.1	0.13
0.2	0.28	0.2	0.16
0.3	0.31	0.3	0.19

6 ANALYSIS POPULATION

The analysis populations are defined as follows:

Safety population will include all randomized and dosed participants.

PK population will include all participants with at least one interpretable PK sample.

7 GENERAL ISSUES FOR STATISTICAL ANALYSIS

Descriptive statistics such as number of observations, mean, median, standard deviation, standard error, minimum and maximum will be presented by dose groups for continuous variables (such as age, weight, etc.). The dose groups will include furosemide groups (by dose level and across all dose levels), placebo group and overall. Other descriptive statistics such as counts, proportions, and/or percentages will be presented by dose groups to summarize discrete variables (such as race, sex, etc.).

Missing data will not be imputed in the non-PK analysis of this study.

Patient profile graphs showing chronologically the dosing, PK sampling, laboratory results of interest, risk of BPD, and adverse events for each participant will be developed.

All confidence intervals and tests will use $\alpha=0.05$. Analyses in this study are exploratory or descriptive in nature. No adjustments for multiplicity between endpoints are planned. Analyses will be performed using SAS Software version 9.2 or later.

8 STUDY PARTICIPANTS AND DEMOGRAPHICS

8.1 Disposition of Participants and Withdrawals

All safety participants will be accounted for in this study. Number and percentage by Cohorts and dose groups for the safety population and PK population will also be presented. Also, summaries will include the number and percentage of participants who completed or early terminated the study, classified by reasons for early termination; the number of participants from each study site; and the number and percentage of participants who completed or early terminated the study at each study site. Early termination is defined as:

1. Participant is randomized but does not receive at least 7 days of study product.

2. Participant receives 7-28 days of study product, but does not complete required follow up assessments.

8.2 Demographics and Baseline Characteristics

Demographic and baseline characteristics will be collected during the screening visit. Variables include gestational age (GA) at birth, postnatal age (PNA), post menstrual age (PMA), maternal race, maternal ethnicity, sex, and birth weight. The PMA is calculated by adding up the completed weeks of GA and PNA. Also, respiratory assessment will be conducted at baseline visit. Surfactant therapy administration and antenatal betamethasone use by the participant's mother will also be summarized.

Medical history will be MedDRA coded and summarized by system organ class and preferred term. Medical history will also be summarized in a participant listing which will also include the actual reported medical conditions. The listing will also include system organ class, preferred term and onset date.

8.3 Protocol Violations and Deviations

All protocol deviations will be reported by site and category of deviation and reason for the deviation. A detailed listing of all protocol deviations by participant will be included. Non-participant specific protocol deviations are also collected and these will also be reported by site and category of deviation.

9 SAFETY ANALYSES

Safety will be assessed following initial study-specific procedure e.g., screening blood draws, dosing through 7 days post last study dose and will be assessed by frequency and incidence of all AEs and SAEs. Other safety parameters include clinical laboratory measurements of interest, concomitant medications of interest, physical examination abnormalities and special events of interest: hearing loss, nephrocalcinosis/nephrolithiasis, and respiratory assessment.

Safety summaries will be provided by dose groups based on data from pre-dose and post-dose visits for the safety population. Frequency counts and descriptive statistics will be provided.

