9.1 Adverse Events

An **adverse event** (AE) is any untoward medical occurrence in humans, whether or not considered drug-related, which occurs during the conduct of a clinical trial. (Any change in clinical status, routine labs, x-rays, physical examinations, etc.), that is considered clinically significant by the study investigator is considered an AE.

Suspected adverse reaction is any adverse event for which there is a reasonable possibility that the drug caused the adverse event. A reasonable possibility implies that there is evidence that the drug caused the event.

Adverse reaction is any adverse event caused by the drug.

Serious adverse event or serious suspected adverse reaction or serious adverse reaction as determined by the investigator or the sponsor is any event that results in any of the following outcomes:

1. Death at or before 36 weeks PMA

2. Life-threatening AE (“life-threatening” means that the study participant was, in the opinion of the investigator or sponsor, at immediate risk of death from the reaction as it occurred and required immediate intervention)
3. Persistent or significant incapacity or substantial disruption of the ability to conduct normal life functions
4. Inpatient hospitalization or prolongation of existing hospitalization
5. Important medical event that may not result in one of the above outcomes, but may jeopardize the health of the study participant or require medical or surgical intervention to prevent one of the outcomes listed in the above definition of serious event

All AEs will be coded using the Medical Dictionary for Regulatory Activities (MedDRA) central coding dictionary. All AEs and SAEs will be summarized by dose groups.

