9.2 Clinical Laboratory Evaluations

Hematology and chemistry parameters will be summarized at baseline (prior to first dose) and last dose, as well as change from baseline to last dose. Tables (by dose groups) will present n, mean, median, minimum, and maximum at baseline, last dose, last day of 7-day safety follow-up period, 36 weeks PMA and change from baseline to last dose. A summary of result assessment shifts from baseline to last dose will be given for each dose group for each parameter. Each parameter will be coded as abnormal and clinically significant (“ABN, CS”) or abnormal and not clinically significant (“ABN, NCS”). The number and percentage of subjects in each dose group in each shift category from baseline to last dose will be shown for each parameter.

Laboratory values at baseline, last dose and changes from baseline to last dose will also be summarized descriptively by dose groups using box plots. The box will represent the 75th and 25th percentiles and the upper and lower whiskers will represent the 95th and 5th percentiles. Mean, median and outliers will be identified. On each box plot, the number available, mean and median will also be presented numerically.

This will be completed for hematology laboratory test (including platelets) and chemistry laboratory test (including alkaline phosphatase, bicarbonate, bilirubin (direct), bilirubin (total), bilirubin (indirect), BUN, caffeine, calcium (ionized), calcium (total), chloride, creatinine, magnesium, phosphorus, potassium, sodium).

The laboratory events of interest will be summarized by dose groups. The laboratory adverse events of interest are listed in Table 3. Any abnormal laboratory values indicating serum electrolytes, renal dysfunction and other dysfunction are captured as laboratory adverse events of interest.

Table 7: Laboratory event values [4]

Laboratory values	Adverse event	Serious adverse event
Serum electrolytes		
Hypernatremia(Sodium)	150–159 mmol/L	> 159 mmol/L
Hyponatremia(Sodium)	120–124 mmol/L	<120 mmol/L
Hyperchloremia(Chloride)	110–120 mmol/L	> 120 mmol/L
Hypochloremia(Chloride)	80–90 mmol/L	< 80 mmol/L
Hyperkalemia(Potassium)	7.0–7.9 mmol/L	>7.9 mmol/L
Hypokalemia(Potassium)	2.0–2.5 mmol/L	<2.0 mmol/L
High Bicarbonate levels (Bicarbonate)	30–45 mmol/L	> 45 mmol/L

Low Bicarbonate levels(Bicarbonate)	12–14 mmol/L	< 14 mmol/L
Hypercalcemia (iCa)	1.3–1.6 mmol/L	>1.6 mmol/L
Hypocalcemia (iCa)	0.7–1.05 mmol/L	< 0.7 mmol/L

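### The dose-group AE, SAE and laboratory-event tables have no rule that excludes events already present before the first dose

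*SAP*

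**What the plan says.** Adverse events are the primary outcome (SAP section 2.2.1), and three statements decide which of them are tabulated.

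- Section 9 sets the period: "Safety will be assessed following initial study-specific procedure e.g., screening blood draws, dosing through 7 days post last study dose". It adds: "Safety summaries will be provided by dose groups based on data from pre-dose and post-dose visits for the safety population".
- Section 9.1 sets the scope: "All AEs and SAEs will be summarized by dose groups".
- Section 9.2 covers laboratory events: "Any abnormal laboratory values indicating serum electrolytes, renal dysfunction and other dysfunction are captured as laboratory adverse events of interest". They are then summarized by dose group in Table 14.3.2.

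Section 9.2 defines baseline as before the first dose, but uses it only for the continuous summaries, the box plots and the shift tables. The shifts are coded by clinical significance, not by the laboratory event ranges. The safety population (section 6) limits which infants are analysed, not when an event began. No treatment-emergent or onset rule appears anywhere in the SAP.

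Among the exclusion criteria in section 1.1 is "Serum creatinine >1.7 mg/dl < 24 hours prior to randomization". The laboratory event table in section 9.2 puts elevated creatinine at 1.5–2.5 mg/dL for an AE.

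**The concern.** The tables are meant to describe what happens on each dose of furosemide. As written, they also count what was already there when the infant was dosed, so the tabulated incidence mixes the state at entry with on-treatment events.

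Within a randomized cohort such events are noise. The reporting columns are not purely within cohort, however. Section 7 shows furosemide by dose level against one placebo group. Each dose level of 30 comes from a single sequential cohort, while placebo is pooled from 10 infants in each of the three. Balance of screening values across successive cohorts is not assured by randomization, and a difference there would appear as a difference between dose groups. Renal events are of direct interest for this drug, and creatinine is the parameter whose entry limit and event range overlap.

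**Working it through.** **Entry limits against event ranges.** Limits come from section 1.1 and AE ranges from section 9.2.

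| Parameter | Excluded at entry | Laboratory AE range | Can an eligible screening value already be an event? |
|---|---|---|---|
| Creatinine | >1.7 mg/dL | 1.5–2.5 mg/dL | Yes, 1.5–1.7 |
| BUN | >50 mg/dL | 60–100 mg/dL | No |
| Low sodium | <125 mmol/L | 120–124 mmol/L | No |
| Low potassium | ≤2.5 mmol/L | 2.0–2.5 mmol/L | No |
| Bilirubin | indirect >10 mg/dL | 20–30 mg/dL, fraction not stated | Not for the indirect fraction |
| Low calcium | ≤6 mg/dL | ionized, 0.7–1.05 mmol/L | Not directly comparable |
| Chloride, bicarbonate, magnesium, phosphorus, alkaline phosphatase, platelets; high sodium, potassium and calcium | no limit | ranges given | Yes |

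**The plan's own precision figures.** These are the yardstick for size. The Wilson width is 2z√(p(1−p)/n + z²/4n²)/(1 + z²/n) with z = 1.96. For n = 30 it gives 0.222, 0.278 and 0.312 at p = 0.1, 0.2 and 0.3, matching 0.22, 0.28 and 0.31 in Table 2 of section 5. The chance of at least one event at rate 0.05 is 1 − 0.95^30 = 0.785 and 1 − 0.95^90 = 0.990, matching the stated 79% and 99%.

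**Clinical AEs.** The on-treatment period is 35 days ("28 days of study drug plus 7 days of safety monitoring"). Screening laboratory values are taken less than 24 hours before randomization, but the time from randomization to first dose is not given, so I assume 1 to 3 pre-dose days. I also assume a constant hazard and a 35-day incidence of 30%.

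- 1 extra day: 1 − 0.7^(36/35) = 0.307; excess 0.0071 × 30 = 0.2 infant.
- 3 extra days: 1 − 0.7^(38/35) = 0.321; excess 0.0211 × 30 = 0.6 infant.

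The shift of 0.7 to 2.1 percentage points is small beside a Wilson width of 0.31.

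**Laboratory events.** Let b be the share already in range before dosing and t = 10% the post-dose incidence, taken as independent of b. The tabulated rate is 1 − (1 − b)(1 − t). The SAP gives no value for b, so a range is shown.

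| b (assumed) | Infants in range before drug, of 30 | Tabulated rate | Excess infants of 30 |
|---|---|---|---|
| 1% | 0.3 | 1 − 0.99 × 0.90 = 10.9% | 0.27 |
| 3% | 0.9 | 1 − 0.97 × 0.90 = 12.7% | 0.81 |
| 10% | 3 | 1 − 0.90 × 0.90 = 19.0% | 2.7 |

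At the top of the range the shift is 9 percentage points, about 40% of the 0.22 Wilson width at a 10% rate. At the bottom it is negligible.

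**Can a worse-than-baseline rule be applied as the ranges stand?** For low bicarbonate, section 9.2 gives 12–14 mmol/L as an AE and <14 mmol/L as an SAE. A value from 12 to just under 14 falls in both, so worse has no meaning there until the two entries are reconciled.

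**The case against.** - *The start of assessment is stated, so this is a disclosed choice.* That is true, and the effect on clinical AEs is small. Disclosure does not make the dose-group incidence an on-treatment incidence, though.
- *Assessment follows the screening draw, so the screening value itself may lie outside the period, and section 9.1 asks for clinical significance.* This stands for clinically reported AEs. The laboratory-event sentence in section 9.2 carries neither a period nor a significance condition, and Table 14.3.2 is supported by the listings of laboratory measurements. Even if the screening sample is left out, an infant whose creatinine simply stays at its entry level would count at the first post-dose sample.
- *Most entry limits keep infants out of the event range.* This is correct for BUN, low sodium and low potassium. Among the parameters with an entry limit in comparable units, only creatinine overlaps. The rest of the problem lies with parameters or directions that have no limit.
- *Baseline summaries, box plots and shift tables would reveal imbalance.* They would help a careful reader, and the patient profiles show timing one infant at a time. None of these corrects the event count.
- *The day count used for escalation in section 4.1 starts at dosing, which might suggest a contradiction with section 9.* A reader might infer one, but that count measures how complete follow-up is. It is not a rule for counting AEs, so the point does not rest on it.

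**Conclusion.** The point holds as a gap in the tabulation rule. As written, events present before any study drug can enter the dose-group AE, SAE and laboratory-event tables. The size is small for clinical AEs (0.2 to 0.6 infant in 30, assuming 1 to 3 pre-dose days, a constant hazard and 30% incidence). It is undetermined for laboratory events: 10% reads 10.9% to 19.0% if 1% to 10% of infants enter in range, assuming independence. The documents do not show that any comparison is actually biased.

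A reader might infer more about deaths, which the SAP does not support. Section 9.1 lists "Death at or before 36 weeks PMA" among the outcomes that make an event serious, while section 9 ends assessment 7 days after the last dose. One defines seriousness and the other a period; an event that starts in the period and is fatal by 36 weeks satisfies both, so the limits do not conflict. Whether a death from a later event is recorded is commonly protocol content, and the SAP tabulates SAEs as determined by the investigator or sponsor. It therefore gives no ground for saying that SAE counts would differ between programmers. Nor can such deaths be sized, because the only death figure is 11% for one illustrative infant in section 10.2.

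It would also be wrong to say that deaths go unreported. No table title in section 13 names death, but deaths can appear in disposition (Table 14.1.1.1) and among SAEs (Table 14.3.1.3). What remains is presentational: the BPD categories in section 10.1 are defined among survivors, and a death count would show who is missing from them. It would not turn observed BPD into the predicted risk of section 10.2, which is a different quantity.

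**What to change.** 1. In section 9.1, restrict Tables 14.3.1.1–14.3.1.7 to events that start or worsen after the first dose.
2. In section 9.2, count a post-dose laboratory event in Table 14.3.2 only if its category is worse than that of the last pre-dose value. Count a post-dose event with no pre-dose value, but flag it as baseline unknown; this matters for parameters without an entry limit, and section 7 rules out imputation.
3. List pre-dose events separately.
4. Reconcile the overlapping low-bicarbonate AE and SAE ranges before applying item 2 to bicarbonate.
5. As a minor addition, show all-cause deaths by dose group through 36 weeks PMA beside Table 14.2.1.

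The cost is some wording, an onset flag, one listing and one table row. No new data are needed: the patient profiles already place dosing and AEs in time order, and death is already to be assessed (section 2.2.3). The entry criteria and SAE definition are untouched, and no laboratory range other than low bicarbonate needs attention. The rules should be settled before unmasking, which section 4.3 places after data lock.

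There are two downsides. Pre-dose events, including any harm from screening procedures, move to a listing where a reader must look for them. A rise that stays within one category will not count as a laboratory event, although the change-from-baseline summaries will still show it.
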